STUDY TREATMENT	
Carfilzomib will be administered intravenously (IV), using the same method, dose level and frequency as administered in the last cycle of the subject's previous carfilzomib study; carfilzomib doses will be administered on Days 1, 2, 8, 9, 15, and 16 of a 28-day cycle (or the same dose level and frequency as administered at the last visit of the prior carfilzomib study) until disease progression and discussion with the Onyx Medical Monitor, diagnosis of new malignancy, unacceptable toxicity, Investigator discretion, voluntary withdrawal, or commercial availability of carfilzomib. Each dose will consist of Carfilzomib for Injection administered on a mg/m² basis. Subjects with a body surface area (BSA) > 2.2 m² will receive a dose based upon a 2.2 m² BSA. Dosing will be continued or modified based upon clinical and laboratory findings.
 
Decreased carfilzomib dosing frequency to include dosing on Days 1, 2, 15 and 16 (eg, every other week dosing schedule), will be permitted at the discretion of the Investigator; the Onyx Therapeutics Medical Monitor may be consulted as needed. Carfilzomib dose reductions for toxicity, to a minimum dose of 11 mg/m², will be permitted following discussion with the Medical Monitor, as needed. Missed doses of carfilzomib will not be made up.
 
Dose escalations above the original dose level are permitted.
 
For subjects with evidence of disease progression, the Onyx Medical Monitor must be consulted prior to the dose escalation or termination from study.
 
Acyclovir or valacyclovir should be given to all subjects with a history of herpes simplex or zoster, per institutional prophylaxis guidelines, unless contraindicated.

PRIMARY ENDPOINT	
• Safety
SECONDARY ENDPOINTS	
• Overall Survival (OS)• Progression Free Survival (PFS)• Time to Progression (TTP)

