1 INTRODUCTION

1.1 CARFILZOMIB BACKGROUND

Carfilzomib (PR-171) is a tetrapeptide ketoepoxide-based selective inhibitor of the chymotrypsin-like activity of the 20S proteasome ([Demo 2005](#)). Carfilzomib is structurally and mechanistically different from the dipeptide boronic acid proteasome inhibitor bortezomib, which is currently approved for use in the treatment of patients with multiple myeloma ([Demo 2005](#), [Velcade 2008](#)). In preclinical studies, carfilzomib demonstrates potent anti-tumor activity in a variety of tumor models, including multiple myeloma (MM) ([Demo 2007](#), [Ivancsits 2006](#), [Kuhn 2007](#)).

1.2 PHASE 1 AND 2 EXPERIENCE WITH CARFILZOMIB IN HEMATOLOGIC MALIGNANCIES ([Carfilzomib IB 2010](#), [Stewart 2007](#), [Onyx Data on File](#))

Phase 1 clinical trials of carfilzomib have been conducted in subjects with hematological tumors, including MM, Waldenström's macroglobulinemia, non-Hodgkin's lymphoma (NHL), and Hodgkin's lymphoma. In a completed study (PX-171-001), carfilzomib dosing ranged from 1.2 mg/m² to 20 mg/m² daily for 5 consecutive days (QDx5) followed by 9 days' rest, in cycles repeated every 14 days. Dose-limiting toxicities (DLTs) associated with the highest dose (20 mg/m²) were Grade 4 thrombocytopenia and Grade 3 febrile neutropenia, and the maximum tolerated dose (MTD) was established at 15 mg/m².

In a completed Phase 1 Study PX-171-002, doses ranging from 1.2 mg/m² to 27 mg/m² are administered on consecutive day dosing (QDx2) twice weekly for 3 weeks, followed by 12 days rest, in cycles repeated every 28 days. DLTs observed at the highest dose (27 mg/m²) included thrombocytopenia and hypoxia, therefore the MTD was established at 20 mg/m². Observations of fever, chills, and rigors, and an elevated creatinine (Grade 2) observed on Day 2 of the 27 mg/m² cohort prior to dosing in this part of the study, led to the development of a stepped-up dosing regimen wherein carfilzomib administration is initiated with a dose at 20 mg/m² followed by escalation to 27 mg/m² after the first cycle.

The most common non-hematologic toxicity events reported from the Phase 1 studies are generally mild, low-grade nausea, diarrhea, dyspnea, headache, and constipation. A Grade 3

or 4–thrombocytopenia may occur in subjects with preexisting low platelets, with recovery occurring between treatments. Grade 3 or higher neutropenia and anemia have also been reported, but less frequently than thrombocytopenia.

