Objective responses including partial responses (PRs) (50%–90% decreases in M-protein) and minimal responses (MRs) (25%–49% decreases in M-protein) were seen in several subjects with plasma cell dyscrasias in both studies. The responses have been durable with PRs on average of 9 months. In addition, both MM and NHL subjects have had stable disease (SD), exceeding 1 year in some cases. Carfilzomib has also shown activity against refractory MM, solid tumors, and 1 mantle cell lymphoma subject with gastrointestinal lymphoma involvement that achieved an unconfirmed complete response (CRu).

The use of carfilzomib in combination with lenalidomide and dexamethasone is being evaluated in a Phase 1b dose escalation Study PX-171-006 in relapsed MM subjects. The study will evaluate the MTD of this combination regimen.

Two Phase 2 studies are ongoing, one for relapsed refractory MM and another in MM subjects relapsed following 1–3 prior therapies. In these studies, tumor lysis syndrome (TLS) has been observed in 4 of 77 subjects treated at the 20 mg/m² dose. Guidelines for the investigator were subsequently implemented for the prevention and management of TLS in ongoing studies.

In May 2009, a MM arm was added to the PX-171-007 study to explore carfilzomib given as a 30-minute infusion. MM subjects receiving carfilzomib administered over 30 minutes have dose escalated to 20/36 mg/m² (4 subjects) and 20/45 mg/m² (3 subjects) without dose-limiting toxicities.

1.3 PHASE 1 AND 2 EXPERIENCE WITH CARFILZOMIB IN SOLID TUMORS ([Carfilzomib IB 2010, Stewart 2007, Onyx Data on File](#))

Carfilzomib is also being studied as a single agent in a Phase 1b/2 Study PX-171-007 in advanced stage solid tumor subjects who have failed available therapies. Subjects are treated with carfilzomib on the QDx2 schedules using the stepped-up dosing regimen previously described. A Phase 1b dose escalation portion has been completed, demonstrating that

administration of 20 mg/m² on Days 1 and 2 followed by 36 mg/m² on subsequent days is well tolerated.

A Simon 2-stage open label study of 70 patients with 5 cohorts was initiated as the Phase 2 portion in April 2008. The cohorts were stratified according to solid tumor disease type. The objective of this portion of the trial was to estimate overall response to 4 cycles of carfilzomib. This portion would only proceed to stage 2 if 1 PR or better occurred after 16 weeks in a cohort.

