1.5 DOSE RATIONALE

Carfilzomib will be administered intravenously (IV) using the same method, dose level and frequency as administered in the last cycle of the subject's previous carfilzomib study.

A carfilzomib dosing schedule on Days 1, 2, 8, 9, 15, and 16 of a 28-day cycle (or the same dose level and frequency as administered at the last visit of the prior carfilzomib study) will be employed and evaluated for long-term safety and efficacy. Subjects will remain at the same dose level and frequency as their previous study because the dose has been shown to be tolerable in the individual subject.

The option will be available to reduce the dosing frequency to Days 1, 2, 15, and 16 of a 28-day cycle (eg, twice a week, every other week). Reductions in dosing frequency will be made at the discretion of the Investigator in consultation with the Medical Monitor.

Dose escalations beyond the original dose level up to the maximum tolerated dose established in primary carfilzomib studies may be permitted following discussion with the Medical Monitor for subjects whose disease progresses on the extended carfilzomib treatment regimen.

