6.2 DOSE MODIFICATION GUIDELINES

6.2.1 DOSE FREQUENCY AND DOSE LEVEL REDUCTIONS

Subjects enrolled in this protocol will begin treatment at the same carfilzomib dose level, frequency and method as the last dose received on their previous study. Dose levels are as follows:

[figure not shown]
Table 1: Carfilzomib for Injection Dose Levels

Carfilzomib Dose Levels
11 mg/m ²
15 mg/m ²
20 mg/m ²
27 mg/m ²
36 mg/m ² *
45 mg/m ² *
56 mg/m ² *

* Dose level for 30-minute infusion

Dose frequency reductions will be allowed at the discretion of the Investigator in consultation with the Medical Monitor. The dose frequency can be reduced to carfilzomib administration on Days 1, 2, 15, and 16 (eg, every other week dosing) of a 28-day cycle, and continued until conditions in section 3.4 are met.

Dose level reductions, to a minimum dose of $11 \text{ mg}/\text{m}^2$, for toxicity will also be permitted; the Medical Monitor may be consulted as needed. Missed doses of carfilzomib will not be made up. Doses of carfilzomib may be rescheduled by up to 48 hours if the scheduled administration falls upon a holiday. Anticipated delays of a scheduled carfilzomib dose by more than 1 day should be discussed beforehand with the Medical Monitor. A dose reduction guideline diagram is as follows:

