6.2.7 DOSE ESCALATION RULES

Dose escalations beyond the original dose level up to the maximum tolerated dose established in primary carfilzomib studies may be permitted following discussion with the Medical Monitor.

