Synopsis: PROCEDURES Efficacy Measures	For subjects with MM entering the extended study with stringent complete response (sCR), complete response (CR), or very good partial response (VGPR), a bone marrow biopsy for cytogenetic and FISH analyses will only be required upon the establishment of disease progression.	For subjects with MM entering the extended study with stringent complete response (sCR), complete response (CR), or very good partial response (VGPR), a bone marrow biopsy for cytogenetic and FISH analyses will also be optional upon the establishment of disease progression.	Revision. To allow bone marrow biopsies for cytogenetic and fluorescence in situ hybridization (FISH) to be optional, rather than required, upon the establishment of disease progression for subjects with MM. To accommodate subjects where bone marrow biopsies are unfeasible or unsafe to obtain.
Section 6.2.1 Dose Frequency and Dose Level Reductions	Carfilzomib Dose Levels 11 mg/m ² 15 mg/m ² 20 mg/m ² 27 mg/m ² 36 mg/m ² * 45 mg/m ² * * Dose level for 30-minute infusion	Carfilzomib Dose Levels 11 mg/m ² 15 mg/m ² 20 mg/m ² 27 mg/m ² 36 mg/m ² * 45 mg/m ² * 56 mg/m²* * Dose level for 30-minute infusion	Addition. A dose level is added since subjects can escalate up to 56 mg/m ² based on dose levels administered in PX-171-007.
Section 6.4.1 Required Concomitant Medication	A proton-pump inhibitor will be used orally daily to prevent peptic disease.	Deleted	Revision. Proton-pump inhibitors are not a required concomitant medication.

Section No.	Amendment 2	Amendment 3	Rationale
Section 7 Study Tests and Observations	These data will not be routinely collected .	These data will not be routinely recorded on CRFs .	Clarification. These data may be collected, but will not be routinely recorded on CRFs.

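### The dose-escalation rule differs between the synopsis and protocol sections 1.5 and 6.2.7 and has no mg/m² ceiling, and the SAP does not define the new baseline after a dose or frequency increase alone

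*Protocol*

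**What the plan says.** **Protocol.** Three places state the escalation rule.

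- Synopsis, Study Treatment: "Dose escalations above the original dose level are permitted". A separate sentence adds: "For subjects with evidence of disease progression, the Onyx Medical Monitor must be consulted prior to the dose escalation". No upper limit is given.
- Section 1.5, Dose Rationale: escalation up to the MTD of the primary studies, after discussion with the Medical Monitor, "for subjects whose disease progresses on the extended carfilzomib treatment regimen".
- Section 6.2.7, Dose Escalation Rules: "Dose escalations beyond the original dose level up to the maximum tolerated dose established in primary carfilzomib studies", after discussion with the Medical Monitor, with no condition on progression.

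On the MTD, section 1.2 gives 15 mg/m² for five-consecutive-day dosing (PX-171-001). For twice-weekly consecutive-day dosing (PX-171-002) it says "therefore the MTD was established at 20" mg/m². Section 1.3 reports that 20 followed by 36 mg/m² "on subsequent days is well tolerated", and that work to determine an MTD for the 30-minute infusion is ongoing. Table 1 in section 6.2.1 lists 11, 15, 20, 27, 36, 45 and 56 mg/m², the last three marked "Dose level for 30-minute infusion".

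**SAP.** Section 5.5 mentions added antitumor agents and increases in carfilzomib dose or frequency, both for concern about progression. It then takes the measurements made when new agents are added as the new baseline. Sections 7.7.2 and 7.7.3 recalculate PFS and TTP when the baseline is reset by new therapy or by an increase in dose or frequency, and give no reason for the increase as a condition.

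**The concern.** Safety is the primary endpoint, and escalation beyond the original dose is where this study leaves the reasoning of section 1.5, which rests on each subject having already tolerated the dose. A site working from the synopsis would see no ceiling, and no Medical Monitor step for a subject without progression. A site working from section 6.2.7 would see both, but could not turn the ceiling into a number.

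On the analysis side, the baseline sets both the start of the PFS/TTP clock and the reference value for progression. If the SAP does not say which measurement is the baseline after an increase, or whether re-escalation after toxicity counts as an increase, two programmers can produce different times and different event statuses for the same subject.

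**Working it through.** The plan has no figure to reproduce here. The check is a comparison of texts, followed by two small illustrations with assumed data.

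**1. The escalation rule side by side**

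| | Who may escalate | Medical Monitor | Ceiling |
|---|---|---|---|
| Synopsis | Any subject | Stated only with evidence of progression | None stated |
| Section 1.5 | Subjects who progress | Discussion needed | MTD of primary studies |
| Section 6.2.7 | Any subject | Discussion needed | MTD of primary studies |

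On who may escalate, section 1.5 is the outlier. On discussion and ceiling, the synopsis is.

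**2. Turning the ceiling into a number**

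- Twice-weekly schedule, the only MTD stated: 20 mg/m². Section 1.2 then describes stepping up to 27 mg/m², a dose at which dose-limiting toxicities had been seen.
- 30-minute infusion: no MTD yet established, according to section 1.3.
- Table 1 maximum: 27 mg/m² without the 30-minute mark, 56 with it.
- Ratios: 27/20 = 1.35 and 56/20 = 2.8.

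Section 6.2.7 does not refer to Table 1. The link between 56 mg/m² and escalation appears only in the rationale column of Appendix F: "A dose level is added since subjects can escalate up to 56" mg/m². That explains why the level is in Table 1, but it is not an operative dosing rule.

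**3. The SAP reset rule side by side**

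| | Trigger | New-baseline measurement |
|---|---|---|
| SAP 5.5 | Added agent, or dose/frequency increase, for concern about progression | Given for added agents only |
| SAP 7.7.2, 7.7.3 | New therapy, or dose/frequency increase, no reason given | Not given |

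Two gaps follow. After an increase alone, no measurement is named. And because 7.7.2 and 7.7.3 give no reason for the increase, re-escalation after a toxicity reduction (protocol 6.2.2 and 6.2.3) falls within their literal wording.

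**4. Illustration: which measurement is the baseline.** Appendix D requires a rise in serum M-protein of at least 25% and at least 0.5 g/dL, so the threshold from baseline b is max(1.25b, b + 0.5). Assume 2.0 g/dL at the last scheduled assessment and 2.4 g/dL on the day of the increase.

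- b = 2.0: max(2.5, 2.5) = 2.5 g/dL.
- b = 2.4: max(3.0, 2.9) = 3.0 g/dL.

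A later value from 2.5 to just under 3.0 is progression on one choice and not on the other.

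**5. Illustration: re-escalation after toxicity.** Without delays, Cycle k Day 1 is study day 28(k − 1) + 1. Cycle 6 is day 141, Cycle 7 day 169, Cycle 9 day 225. Assume re-escalation to the original dose on day 169 and progression found on day 225.

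- No restart: PX-171-010 PFS = 225 − 1 + 1 = 225 days, event.
- Restart: the first period is censored at the last assessment (day 141 if only scheduled assessments were done, day 169 if one was done that day). A new PFS of 225 − 169 + 1 = 57 days, event, then follows.

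The M-protein values and dates are assumptions. They show that the gaps can change a subject's result, not how often this would happen.

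**The case against.** **Table 1 is not an escalation ceiling.** It sits under dose reductions and lists levels at which rollover subjects may enter. Section 6.2.7 sets the ceiling by reference to the primary studies, whose own documents may define an MTD for each regimen. This stands. A reader might infer that Table 1 contradicts the MTD, or that the plan allows doses known to be unsafe; the documents support neither. What remains is that the protocol gives the site no usable number, and its own background text points to several.

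**SAP 5.5 and 7.7.2/7.7.3 do not contradict each other on whether an increase resets the baseline.** The conditional sentence in 5.5 follows both triggers and can cover both, and 7.7.2 and 7.7.3 name the increase openly. This also stands. A reader might infer a direct conflict, but a no-reset reading of 5.5 runs against the two later sections. The defect is the missing measurement.

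**Re-escalation may already be excluded.** The later sections recalculate when the baseline is reset, and 5.5 ties increases to concern about progression. That is a sensible reading, but 7.7.2 and 7.7.3 do not repeat the condition, so it should be written down.

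**The endpoints are descriptive.** No hypothesis is tested, and PFS and TTP are secondary. This limits the weight of the SAP part but does not affect the dosing rule.

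**Conclusion.** The protocol inconsistency is established from the text alone. Three statements of one rule differ on eligibility, Medical Monitor involvement and ceiling, and the ceiling has no value in mg/m². For twice-weekly dosing, the values a reader could take from the protocol run from 20 to 56 mg/m², across infusion methods. This should be corrected because it governs dosing in a study whose primary endpoint is safety.

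The SAP part is narrower: an undefined baseline measurement after a dose or frequency increase alone, and no explicit exclusion of re-escalation after toxicity.

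A reader might go further and conclude that PFS and TTP are overstated by a calculable amount, because subjects whose regimen is changed on suspicion of progression are censored first. Such censoring could be informative, but the documents do not give the share of subjects affected, the false-alarm rate or the expected medians. The SAP plans Kaplan-Meier quartiles by cohort and regimen, so a bias computed for a pooled time point would describe an estimate it does not report. The censoring itself is already covered by the SAP Table 1 row for subjects alive without documented progression. The size of any bias is therefore unknown.

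**What to change.** 1. **Protocol.** Make section 6.2.7 the single rule and align the synopsis and section 1.5 to it. Every escalation beyond the original dose level needs prior discussion with the Medical Monitor and may not exceed a sponsor-confirmed limit in mg/m² for each infusion method. Whether progression is required is the sponsor's choice, but it must read the same in all three places.
2. **SAP 5.5, 7.7.2 and 7.7.3.** Use one rule: when an antitumor agent is added, or carfilzomib dose or frequency is increased beyond the original level for concern about progression, the last disease assessment on or before the date of the change becomes the new baseline. Re-escalation to the original level after a toxicity reduction does not reset it.
3. **Optional.** Report by cohort how many subjects had a baseline reset without documented progression, with a descriptive sensitivity PFS/TTP that counts the change as an event. State that this overcounts events where the concern was a false alarm.

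**Cost.** Item 1 is a short amendment, but section 11.2 requires written IRB/IEC approval before it is implemented, across about 50 centers. Item 2 is one rule in three SAP sections. Its limitation is that, with assessments required only every 3 months, the last one may be up to about 3 months old at the change. No new data collection is expected, since SAP 7.4 says reasons for regimen change are on a case report form; the sponsor should check that the form identifies concern about progression as a reason. Item 3 adds one count and one descriptive analysis.

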6.3 SAFETY GUIDANCE FOR INVESTIGATORS

6.3.1 SAFETY GUIDANCE

Based upon the experience in Phase 1 studies with carfilzomib, the following observations must be noted:

Physicians administering carfilzomib in subjects with compromised renal function should hydrate appropriately and treat according to calculated CrCl, not on serum creatinine. It is recommended that electrolyte abnormalities judged as clinically significant by the Principal Investigator (or qualified designee) be corrected to \leq Grade 1 or baseline. Renal function and serum creatinine should be monitored prior to dosing. Carfilzomib must be held if a subject presents with a CrCl < 15 mL/min with the following exception: for subjects with CrCl < 15 mL/min at study entry, study drug must be held if CrCl drops $\geq 50\%$ from baseline. Subjects who develop an active infection requiring systemic treatment should not be dosed with carfilzomib until the infection has resolved and the treatment course has been completed. Subjects with \geq Grade 3 neutropenia should not be treated with carfilzomib.

Carfilzomib dosing must be held for Grade 4 thrombocytopenia with bleeding. If platelet counts do not recover, the dose of carfilzomib may be reduced or held according to the Dose Reductions/Adjustments rules outlined in [Section 6.2.2](#). For Grade 4 thrombocytopenia without evidence of active bleeding, platelet transfusions may be used per study site policies and at the discretion of the Investigator or treating physician.

Carfilzomib treatment can cause nausea, vomiting, diarrhea, or constipation, sometimes requiring the use of antiemetics or antidiarrheals. Fluid and electrolyte replacement should be administered to prevent dehydration.

6.4 CONCOMITANT MEDICATIONS

Concomitant medication is defined as any prescription or over-the-counter preparation, including vitamins and supplements.

6.4.1 REQUIRED CONCOMITANT MEDICATION

All subjects with a history of herpes viral infection should receive acyclovir or valacyclovir prophylaxis according to institutional guidelines and the investigator's discretion.

6.4.2 ALLOWED CONCOMITANT MEDICATIONS

Commercially available bisphosphonates are permitted. Subjects may receive antiemetics and antidiarrheals as necessary, but these should not be administered unless indicated.

Colony-stimulating factors may be used if neutropenia occurs but should not be given prophylactically.

Subjects may receive platelet transfusions in accordance with institutional guidelines.

Red blood cell (RBC) transfusions or supportive care with erythropoietin or darbepoetin alfa, in accordance with institutional guidelines, is also permitted.

Subjects who received 4 mg dexamethasone prior to carfilzomib dosing on an ongoing basis during their previous carfilzomib treatment protocol may continue to receive 4 mg dexamethasone prior to carfilzomib dosing on the current protocol at the investigator's discretion.

The addition of certain approved agents with known antitumor activity is permitted if there is concern for disease progression and per Investigator discretion in consultation with the Onyx Medical Monitor.

